4. Eastern Cooperative Oncology Group Performance Status of 0 or 1 (see [APPENDIX 1](#))
5. Adequate bone marrow function at screening, characterized by the following:
- a. absolute neutrophil count (ANC) \geq $1.0 \times 10^9/L$

- b. platelets $\geq 75 \times 10^9/L$
 - c. hemoglobin ≥ 9.0 g/dL
Note: Transfusions will be allowed to achieve the acceptable hemoglobin value.
6. Adequate renal function characterized by serum creatinine $\leq 1.5 \times$ upper limit of normal (ULN) or calculated or directly measured creatinine clearance ≥ 50 mL/min at screening
 7. Adequate hepatic function at screening, characterized by the following:
 - a. serum total bilirubin $\leq 1.5 \times$ ULN and < 2 mg/dL
Note: Patients who have a total bilirubin level $> 1.5 \times$ ULN will be allowed if their indirect bilirubin level is $\leq 1.5 \times$ ULN
 - b. ALT and/or AST $\leq 2.5 \times$ ULN, or $\leq 5 \times$ ULN in presence of liver metastases
 8. For male patients and female patients of childbearing potential, agreement to use an acceptable method of contraception as defined in the protocol (see [Section 5.3](#)) from the start of study treatment until 7.5 months after the last dose of pembrolizumab for males and until 5.5 months after the last dose of pembrolizumab for females
Note: Women are considered not of childbearing potential if they have had 12 months of natural (spontaneous) amenorrhea with an appropriate clinical profile (e.g., age appropriate, history of vasomotor symptoms) or have had surgical bilateral oophorectomy with hysterectomy or tubal ligation at least 6 weeks prior to Screening. In the case of oophorectomy alone, only when the reproductive status of the woman has been confirmed by follow-up hormone level assessment is she considered not of childbearing potential.
 9. For females of childbearing potential only, negative serum human chorionic gonadotropin (hCG) pregnancy test result at baseline and nonlactating
 10. Willingness and ability to comply with scheduled visits, treatment plan, laboratory tests, and other study procedures
 11. **Phase 2 only:** Availability of a fresh biopsy (preferred) or an archival tumor sample from the most recent sample available. Between 10 to 15 slides or an archival block are required.

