6.3.2 ARRY-382

General guidelines for dose modifications of ARRY-382 are provided in [Table 8](#). However, Investigators are to use their judgment when assessing the clinical significance of individual AEs.

Table 8: Recommended Dose Modifications for ARRY-382 Treatment-Related Adverse Events

Severity of Event	Action to be Taken
Grade 0-1	
 • Maintain ARRY-382 dose level and provide treatment to control symptoms, if applicable.
Grade 2	
 • Provide treatment to control symptoms, if applicable. If the symptoms cannot be controlled, withhold ARRY-382 until resolution or return to baseline. Then, resume at the original dose. • In the event of a persistent Grade 2 AE that is not responsive to treatment measures or that prevents the patient from resuming treatment, ARRY-382 treatment may be resumed at the next lower dose level. • In the event of irAEs: 
 ○ At first occurrence, withhold ARRY-382 until resolution or return to baseline. Then, resume treatment with ARRY-382 at the same dose level. ○ At second occurrence, withhold ARRY-382 until resolution or return to baseline. Then resume treatment with ARRY-382 at the next lower dose level. ○ At third occurrence, discontinue ARRY-382.
Grade 3	
 • Withhold ARRY-382 until the AE recovers to resolution, or return to baseline. Then, resume treatment with ARRY-382 at the next lower dose level.^a • In the event of a Grade 3 QTcF prolongation or > 60 msec increase in QTcF interval seen on ≥ 2 ECGs (on at least 2 separate ECGs). 
 ○ At first occurrence, interrupt ARRY-382 until QTcF decreases below 500 msec. Then resume treatment at next lower dose level ○ At second occurrence, discontinue ARRY-382.
Grade 4	
 • Discontinue administration of ARRY-382^b
Dose delay > 21 days due to AEs and not underlying disease progression, concomitant illness, or non-medical issues	
 • Discontinue administration of ARRY-382 (unless it is in the best interest of the patient to continue treatment, as judged by the Investigator)

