ALT or AST elevations	
 • ALT or AST > 8 × ULN ≤ 20 × ULN (Grade 3) 
 ○ Withhold ARRY-382. Resume treatment at the next lower dose level if ALT or AST resolves to Grade 1 or baseline (or ≤ 5 × ULN in presence of liver metastases) in ≤ 7 days ○ Discontinue ARRY-382 if ALT or AST > 8 × ULN for > 7 days • ALT or AST ≥ 5 × ULN and ≤ 8 × ULN (Grade 3) 
 ○ Withhold ARRY-382. Resume treatment at the next lower dose level if ALT or AST resolves to Grade 1 or baseline in ≤ 14 days ○ Discontinue ARRY-382 if ALT or AST > 5 × ULN for > 14 days • ALT or AST > 3 × ULN and bilirubin levels ≥ 2 × ULN or an INR > 1.5 unless clearly attributable to disease progression 
 ○ Discontinue ARRY-382 • ALT or AST > 20 × ULN (Grade 4) 
 ○ Discontinue ARRY-382

AE = adverse event; ALT = alanine aminotransferase; AST = aspartate aminotransferase; CK = creatine kinase; ECG = electrocardiogram; INR = international normalized ratio; irAE = immune-related adverse event; QTcF = QT interval corrected for heart rate using Fridericia's formula; ULN = upper limit of normal

- ^a The following exceptions apply: 1) ARRY-382 should not be withheld for increased CK unless it is associated with an increase in creatinine $\geq 1.5 \times$ the baseline value for creatinine OR until the CK increase remains \geq Grade 3 for > 7 days. 2) In the event of Grade 3 nausea, vomiting or diarrhea, the patient can continue at the same dose of ARRY-382 if the patient is responsive to treatment measures.
- ^b A patient with a Grade 4 AE may resume treatment at the next lower dose level if the AE recovers to Grade 0 or 1 and, if in the opinion of the Investigator and Sponsor, the patient can be monitored for recurrence of AE.

Patients should be evaluated weekly, at a minimum for nonlaboratory, ARRY-382-related toxicities until resolution or return to baseline, and then at least monthly until return to baseline, whichever comes first. For abnormal laboratory values that qualify as AEs, patients should be followed twice weekly until resolution or return to baseline.

Doses of ARRY-382 withheld during a cycle will not be made up. When a dose reduction is required because of AEs, no dose re-escalation will be permitted for the duration of study treatment.

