7.5.2 Clinical Laboratory Tests

Clinical laboratory tests include hematology, coagulation, clinical chemistry, thyroid panel, and urinalysis ([Table 9](#)) and will be collected at the time points specified in [Table 10](#) and [Table 11](#). It is expected that local laboratories will be used for all protocol-specified and unscheduled laboratory tests related to safety. Depending on the availability of certain tests at local laboratories, some protocol-specified laboratory tests may be performed outside of local laboratories.

Table 9: Clinical Laboratory Tests

Hematology	Chemistry	Urinalysis	Others
Hemoglobin	BUN	Appearance	
 • HBsAg and HCV serology (RNA, qualitative if serology positive) (screening only) • Serum or urine pregnancy test^b (females of childbearing potential only)
Hematocrit	Urea	Color	
RBC	Uric acid	Specific gravity	
Platelets	Creatinine	pH	
WBC	Creatinine clearance ^a	Myoglobin ^c	
Neutrophils	Total protein	Protein	
Lymphocytes	Albumin	Glucose	
Monocytes	Alkaline phosphatase	Ketones	
Eosinophils	AST	Blood	
Basophils	ALT	Nitrite	
	Lactate dehydrogenase	Leukocyte esterase	
	Total bilirubin	If urinalysis is abnormal, then microscopy:	
	Indirect bilirubin	
 • WBC • RBC • Bacteria • Epithelial cells • Casts 	
	Direct bilirubin (if total bilirubin values are above normal)		
Coagulation			
INR	Amylase		
PT	Lipase		
aPTT/PTT	Aldolase		
	CK		
Thyroid Panel	CK isoenzymes ^c		
TSH	Glucose		
T3, free	Sodium		
T4, free	Potassium		
	Chloride		
	Bicarbonate		
	Calcium		
	Magnesium		
	Phosphorus		

ALT = alanine aminotransferase; aPTT = activated partial thromboplastin time; AST = aspartate aminotransferase; BUN = blood urea nitrogen; CK = creatine kinase; HBsAg = hepatitis B surface antigen; HCV = hepatitis C virus; INR = International Normalized Ratio; PT = prothrombin time; PTT=partial thromboplastin time; RBC = red blood cells; RNA = ribonucleic acid; T3 = triiodothyronine; T4 = thyroxine; TSH = thyroid-stimulating hormone; WBC = white blood cells

^a Creatinine clearance will be calculated using the Cockcroft-Gault formula $[(140 - \text{age}) * \text{body mass (kg)} / \text{creatinine (mg/dL)} * 72] * 0.85$ for females or 1.00 for males.

^b Serum pregnancy test required at screening only; serum or urine pregnancy tests will be allowed at subsequent time points.

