Appendix 3 Child Pugh Classification

Measure	Points		
	1	2	3
Bilirubin (mg/dL)	<2.0	2.0-3.0	>3.0
Albumin (g/dL)	>3.5	2.8-3.5	<2.8
PT (INR)	<1.7	1.7-2.3	>2.3
Ascites	Absent	Mild to moderate	Severe/refractory
Encephalopathy (grade)*	Absent	Mild (1-2)	Severe (3-4)

*Grade 0: normal consciousness, personality, neurological examination, electroencephalogram
Grade 1: restless, sleep disturbed, irritable/agitated, tremor, impaired handwriting, 5 cps waves
Grade 2: lethargic, time-disoriented, inappropriate, asterixis, ataxia, slow triphasic waves
Grade 3: somnolent, stuporous, place-disoriented, hyperactive reflexes, rigidity, slower waves
Grade 4: unrousable coma, no personality/behavior, decerebrate, slow 2-3 cps delta activity

Class A=5-6 points; Class B=7-9 points; Class C=10-15 points; Abbreviations: PT, prothrombin time; INR, International Normalized Ratio.

US Department of Health and Human Services, Food and Drug Administration. Guidance for Industry: Pharmacokinetics in Patients with Impaired Hepatic Function: Study Design, Data Analysis, and Impact on Dosing and Labeling. May 2003. Available from: <<https://www.fda.gov/downloads/drugs/guidancecomplianceregulatoryinformation/guidances/ucm072123.pdf>> (Accessed on 06 November 2017).

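### The bilirubin exception in inclusion criterion 7a is tied to the indirect fraction, so it mainly admits patients whose excess is direct; it also leaves the applicable ULN and the 2 mg/dL limit unclear

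*Protocol*

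**What the plan says.** **Entry.** Criterion 7 in Protocol 5.2.1 asks for adequate hepatic function at screening. The base rule in 7a is "serum total bilirubin $\leq 1.5 \times$ ULN and < 2 mg/dL". The Note then says that a patient with total bilirubin above 1.5 × ULN "will be allowed if their indirect bilirubin level is" at or below 1.5 × ULN. It sets no ceiling on total or direct bilirubin. Criterion 7b limits ALT and AST to 2.5 × ULN, raised to 5 × ULN "in presence of liver metastases".

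**Other limits at entry.** Exclusion 15 (5.2.2) removes Child Pugh Class B and C. Appendix 3 defines "Class A=5-6 points; Class B=7-9 points; Class C=10-15 points" and scores bilirubin 1 point below 2.0 mg/dL, 2 points from 2.0 to 3.0 and 3 points above 3.0. Exclusion 22 lets the Investigator refuse a patient whose laboratory abnormality may raise the risk of taking part.

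**On treatment.** Table 8 (6.3.2) is titled "Recommended Dose Modifications for ARRY-382 Treatment-Related Adverse Events". One of its rows reads "ALT or AST > 3 × ULN and bilirubin levels ≥ 2 × ULN or an INR > 1.5", with a carve-out for values plainly due to disease progression. The action is to discontinue ARRY-382.

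**Tests.** Table 9 (7.5.2) lists indirect bilirubin, and adds direct bilirubin whenever the total is above normal.

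**The concern.** A criterion meant to secure liver function uses total bilirubin as its measure. The Note removes the limit on that measure and replaces it with a limit on one component only. The component left free is the direct fraction, so a patient can have any excess of direct bilirubin and still use the exception. A patient whose excess is indirect generally cannot. The exception therefore works against the criterion it modifies.

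Two things are at stake. The first is safety at entry. Part A recorded a DLT of Grade 3 AST/ALT and bilirubin increase in one patient at 400 mg (Protocol 2.3.1), so bilirubin with transaminases is a signal the trial has reason to watch. The second is interpretation. The hepatic toxicity tables in SAP 7.6.5 count newly occurring values, including ALT or AST above 3 × ULN with total bilirubin above 2 × ULN. On the natural reading, a patient already in that category at baseline cannot enter it as new.

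**Working it through.** There is no sample size, power or error-rate figure behind this point, so no figure of the plan has to be reproduced. The check applies the written rules to bilirubin profiles.

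**Inputs.** From the Protocol: 7a and its Note, 7b, exclusion 15 with Appendix 3, and the Table 8 row. The documents give no ULN for bilirubin. I assume a total ULN of 0.9 to 1.3 mg/dL, and an indirect ULN that is either fraction-specific or equal to the total ULN.

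**Step 1: whom the Note admits.** Write T = D + I (total, direct, indirect), with upper limits U_T, U_D and U_I. The Note requires T > 1.5 U_T and I ≤ 1.5 U_I.

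- If U_T = U_D + U_I, then D = T − I > 1.5 U_T − 1.5 U_I = 1.5 U_D. Every patient admitted by the Note then has direct bilirubin above 1.5 × ULN.
- If the total ULN is applied to the indirect fraction, the Note admits 1.5 U_T < T ≤ 1.5 U_T + D. A patient with isolated indirect elevation is then admitted only in a band as wide as the direct fraction. With D = 0.2 and U_T = 1.0, that band runs from above 1.5 to 1.7 mg/dL.
- A patient with total 2.2, indirect 2.0 and direct 0.2 mg/dL is refused on either basis with U_T = 1.2. The indirect limit is 1.5 × 1.2 = 1.8 on the total ULN, or 1.5 × 0.9 = 1.35 with an indirect ULN of 0.9.

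**Step 2: what Child Pugh stops.** Bilirubin of 2.0–3.0 mg/dL with the other four items normal scores 2 + 1 + 1 + 1 + 1 = 6, Class A, eligible. Above 3.0 mg/dL the score is 3 + 4 = 7, Class B, excluded. The ceiling is therefore 3.0 mg/dL, and lower if another item scores more than 1.

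**Step 3: overlap with Table 8.** Take a patient with liver metastases and ALT or AST above 3 and up to 5 × ULN, which 7b allows. The bilirubin threshold in Table 8 is 2 × U_T.

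| Assumed U_T (mg/dL) | 1.5 × U_T | 2 × U_T | Overlap in total bilirubin if the 2 mg/dL limit is waived | Overlap if it is kept |
|---|---|---|---|---|
| 0.9 | 1.35 | 1.80 | 1.8–3.0 | 1.8 to below 2.0 |
| 1.0 | 1.50 | 2.00 | 2.0–3.0 | none |
| 1.2 | 1.80 | 2.40 | 2.4–3.0 | none |
| 1.3 | 1.95 | 2.60 | 2.6–3.0 | none |

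Without the Note, T ≤ 1.5 U_T < 2 U_T and the bilirubin threshold cannot be reached, so the Note creates this overlap. The INR alternative in the same row is separate: the only INR limit at entry is through Child Pugh, so that alternative can be matched with or without the Note.

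**Step 4: one patient worked through.** Assume ULNs of 1.2 (total), 0.9 (indirect) and 0.3 (direct). Total is 2.6 mg/dL (2.6/1.2 = 2.2 × ULN), indirect 0.8 (below 1.5 × 0.9 = 1.35), direct 1.8 (6 × ULN). AST is 4 × ULN with liver metastases, and the other Child Pugh items are normal (total 6). If the 2 mg/dL limit is waived, this patient passes 7a by the Note, 7b and exclusion 15, and matches both numeric thresholds in Table 8.

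**The case against.** The strongest reply concerns Table 8. A reader might infer that such a patient must be taken off ARRY-382 on Day 1, so that entry and stopping rules contradict each other outright. The documents do not support that. Section 6.3.2 presents the table as general guidance, subject to Investigator judgment, for treatment-related events. A finding before the first dose belongs in the medical history (10.5). The row exempts values clearly due to progression, which matters for a patient with liver metastases. Other ALT/AST rows accept recovery to baseline, so the table foresees abnormal baselines. What remains is a match of numbers with no stated handling.

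The Note can also be read as waiving only the 1.5 × ULN limb of 7a, since it names only that limb. The 2 mg/dL limit would then stand, and the Table 8 overlap would vanish for any ULN of 1.0 mg/dL or more. That reading is fair, but the text does not settle it.

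It would also be too strong to say that all isolated indirect elevation is refused. The base rule admits it up to its own limits, and Step 1 shows a narrow further band if the total ULN is used. Likewise, the claim that every patient admitted by the Note has raised direct bilirubin needs fraction-specific ULNs that add up.

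Finally, exclusion 22 and the Investigator's review of Day 1 results (7.5.2) offer protection, and the bilirubin signal is one patient at a dose above the 300 mg used in Phase 2. These points limit the likely harm. They rest on case-by-case judgment, however, and do not repair a written rule that points the wrong way.

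**Conclusion.** The point holds on the plain wording. The Note relaxes a hepatic-function criterion mainly for patients whose excess is direct, and no other rule limits direct bilirubin at entry. The written ceiling is a total of 3.0 mg/dL through Child Pugh with the other items normal, unless the 2 mg/dL limit still applies.

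The Table 8 overlap is conditional. It needs liver metastases, ALT or AST above 3 and up to 5 × ULN and, for a ULN of 1.0 mg/dL or more, the reading that the Note also waives the 2 mg/dL limit. On that reading it spans 2.0–3.0 mg/dL at a ULN of 1.0 and 2.4–3.0 at 1.2. All ULN values are assumptions.

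A reader might infer that the fraction named is a slip and that direct bilirubin was meant. The documents state no purpose for the Note, so that cannot be concluded from them. The Simon designs, endpoints and sample sizes are unaffected.

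**What to change.** Amend the Protocol in two places.

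1. Reconcile the 7a Note with the base rule and purpose of criterion 7. State which bilirubin fraction and which ULN the exception is meant to use, and whether the 2 mg/dL limit still applies to patients who use it; or withdraw the Note.
2. Reconcile 7a and 7b with the Table 8 row on ALT/AST combined with bilirubin or INR, so that the handling of eligible baseline values is consistent.

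The clinical rule is for the sponsor to decide, and no threshold is proposed here. The cost is a short edit in an amendment. No new test is needed, because Table 9 already provides both fractions when the total is above normal. The downside is that a few patients may change eligibility status.

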5.2.2 Exclusion Criteria

Patients meeting any of the following criteria are ineligible for enrollment in the study.

1. Prior treatment as follows:

Part A:

- An immune CPI (e.g., PD-1, PD-L1, or CTLA-4 inhibitor)

NOTE: Prior treatment with a CSF-1R or CSF-1 (or macrophage colony-stimulating factor [MCSF]) inhibitor is allowed. For patients with melanoma, prior treatment with ipilimumab is allowed if it was administered as adjuvant therapy and treatment was completed at least 3 months prior to enrollment.

Phase 2:

- A CSF-1R inhibitor or CSF-1 (or MCSF) inhibitor
- prOVCA and PDA patients only: an immune CPI (e.g., PD-1, PD-L1, or CTLA-4 inhibitor)

2. Symptomatic brain metastasis at screening

NOTE: Patients who are asymptomatic will be allowed, regardless of whether they received previous treatment for the metastases. Any brain metastases present at screening must be stable by imaging (e.g., magnetic resonance imaging [MRI] or computed tomography [CT]) demonstrating no evidence of progression at screening; patients must not be receiving anticonvulsant therapy and must have completed treatment with corticosteroids or be taking a decreasing dose of corticosteroids.

3. Active autoimmune disease, documented history of autoimmune syndrome or disease, or a chronic medical condition that requires chronic steroid therapy or immunosuppressive medication

NOTE: Exceptions include patients with vitiligo, resolved childhood asthma/atopy, patients who require intermittent use of bronchodilators or local steroid injections, and patients with a history of hypothyroidism taking a stable dose of replacement therapy. In addition, patients requiring physiological replacement doses of hydrocortisone or its equivalent (i.e., up to 20 mg hydrocortisone [or 5 mg prednisone] in the morning, and 10 mg hydrocortisone [or 2.5 mg prednisone] in the evening) will be considered eligible for the study.

4. Impaired gastrointestinal function or disease that may significantly alter the absorption of ARRY-382 (e.g., ulcerative diseases, uncontrolled nausea, vomiting, diarrhea, malabsorption syndrome, small bowel resection)

5. Presence of risk factors for bowel obstruction or bowel perforation (e.g., history of acute diverticulitis, intra-abdominal abscesses, or abdominal carcinomatosis)
6. History of severe hypersensitivity to mAb
7. Active infection requiring therapy
8. History of pneumonitis or interstitial lung disease
9. Symptomatic ascites or symptomatic pleural effusion

NOTE: For prOVCA patients, paracentesis or pleurocentesis to relieve symptoms prior to and during treatment will be permitted.

10. Leptomeningeal disease
11. Ocular melanoma
12. Use of herbal medications/supplements or any medications or foods that are strong inhibitors or inducers of CYP3A4/5 within 2 weeks before the start of study treatment
13. Clinically significant cardiac disease, including any of the following:
 - a. congestive heart failure requiring treatment (New York Heart Association Grade ≥ 2)
 - b. uncontrolled hypertension per World Health Organization (WHO)/International Society of Hypertension (ISH) 2003 guidelines
 - c. presence of clinically significant and uncontrolled atrial fibrillation
 - d. unstable angina pectoris ≤ 3 months prior to enrollment
 - e. acute myocardial infarction ≤ 3 months prior to enrollment
14. QT abnormality or risk of QT abnormality, as follows:
 - a. a prolonged QTcF ≥ 450 msec at screening (based on average of 3 readings)
 - b. history or evidence of congenital long QT syndrome
 - c. use of concomitant medications that may prolong QT/QTc interval or induce torsades de pointes (see [APPENDIX 2](#)) within 2 weeks before the start of study treatment
15. Impaired hepatic function, defined as Child Pugh ([Schwartz et al 2007](#)) Class B or C (see [APPENDIX 3](#))

16. Previous tumor malignancy within the last 3 years, or has a concurrent malignancy, with the exception of adequately treated basal cell or squamous cell carcinoma, in situ carcinoma of the cervix, in situ breast cancer, or in situ prostate cancer without evidence of active disease for 2 years before enrollment
17. History of thromboembolic or cerebrovascular events, including transient ischemic attacks, cerebrovascular accidents, deep vein thrombosis, or pulmonary emboli within 6 months before enrollment
18. Prior therapy consisting of any of the following:
 - a. cyclical chemotherapy within a period of time that was shorter than the cycle length used for that treatment (e.g., 6 weeks for nitrosourea, mitomycin-C)
 - b. biologic therapy (e.g., antibodies), continuous or intermittent small-molecule therapeutics, or any other investigational agents within a period of time that is ≤ 5 half-lives ($t_{1/2}$) or ≤ 2 weeks (whichever is shorter)
19. Residual Common Terminology Criteria for Adverse Events (CTCAE) \geq Grade 2 side effects of any prior therapy, with the exception of residual Grade 2 alopecia
20. Known history of human immunodeficiency virus (HIV) infection
21. Active hepatitis B (hepatitis B surface antigen-[HBsAg-]reactive) or hepatitis C serology infection (hepatitis C virus [HCV] ribonucleic acid [RNA] [qualitative] will be required if serology is positive)
22. Severe, acute, or chronic medical or psychiatric condition or laboratory abnormality that may increase the risk associated with study participation or study drug administration or that may interfere with the interpretation of study results and, in the judgment of the Investigator, would make the patient an inappropriate candidate for the study

